8 SELECTION AND WITHDRAWAL OF SUBJECTS

The enrollment of eligible subjects is critical to ensure the outcome of the study. Subjects must meet the following criteria to be allowed to participate in this study. Any medical or non-medical conditions of a subject are considered for his/her eligibility.

Before the subject's enrollment in the study, the investigator should review, confirm, and document whether the subject is suitable for participating in the study.

8.1 Inclusion Criteria

Patients must meet all of the following criteria to be eligible.

1. Aged 16-70 years, male or female.
2. With an Eastern Cooperative Oncology Group (ECOG) PS of 0-1. The criterion can be relaxed to 2 points for amputation subjects.
3. Life expectancy of ≥ 3 months.
4. Patients with distant metastasis or locally advanced soft tissue sarcoma that render the patient not suitable for surgical treatment as per the investigator's judgment (pathologically or cytologically diagnosed, except gastrointestinal stromal tumors, osteochondroma, embryonic/acinar rhabdomyosarcoma, Ewing's sarcoma, and intermediate soft tissue tumors without extensive metastasis, such as dermatofibrosarcoma protuberans and inflammatory myofibroblastic sarcoma, see [Appendix 1. The WHO Soft Tissue Tumor Classification \(2013 Edition\)](#) for details).

5. Patients who have not received previous chemotherapy for soft tissue sarcoma, or have benefited from chemotherapy but have recurrence or metastasis more than 6 months after drug discontinuation.
6. With measurable lesion(s) as per RECIST v1.1.
7. All acute toxicities due to previous anti-tumor treatments or surgeries must have resolved to Grade 0-1 (as per NCI CTCAE 4.03) or to the level specified in the inclusion/exclusion criteria before C1D1 (except for toxicities such as alopecia that are deemed by the investigator as not posing safety risks to the patient).
8. With adequate organs and bone marrow functions, as defined below:

Hematology (without blood transfusion, G-CSF, or medication correction within 14 days prior to screening)

- Absolute neutrophil count (ANC) $\geq 1500/\text{mm}^3$ ($1.5 \times 10^9/\text{L}$);
- Blood platelet count (PLT) $\geq 100,000/\text{mm}^3$ ($100 \times 10^9/\text{L}$);
- Hemoglobin (Hb) $\geq 9 \text{ g/dL}$ (90 g/L);

Blood Biochemistry

- Serum creatinine (Cr) $\leq 1.5 \times$ upper limit of normal (ULN), or creatinine clearance (Cockcroft-Gault formula) $\geq 60 \text{ mL/min}$;
- Total bilirubin (TBIL) $\leq 1.5 \times$ ULN;
- Aspartate transaminase (AST) or alanine transaminase (ALT) $\leq 2.5 \times$ ULN; for patients with liver metastasis, ALT and AST should be $\leq 5 \times$ ULN;

Coagulation Function

- International normalized ratio (INR) ≤ 1.5 , prothrombin time (PT) and activated partial thromboplastin time (APTT) $\leq 1.5 \times$ ULN;

Urinalysis

- Urine protein $< 2+$; If urine protein is $\geq 2+$, then the 24-hour urine protein must be $\leq 1 \text{ g}$;

Thyroid function

- Thyroid-stimulating hormone (TSH) \leq ULN; if abnormal, FT3 (T3) and FT4 (T4) levels should be examined, and the subject can be enrolled if FT3 (T3) and FT4 (T4) levels are normal.

9. Female subjects of childbearing potential must have a negative serum pregnancy test within 7 days prior to C1D1, and be willing to use a recognized effective contraceptive measure (such as: intra-uterine contraceptive devices, contraceptive pills, or condoms) during the study and within 3 months after the last dose of the study drug; male subjects with partners of childbearing potential must either be surgically sterilized or agree to take effective contraceptive measures during the study and within 3 months after the last dose of the study drug.
10. Subjects must agree and have signed the informed consent form, be willing and able to follow the scheduled visits, study treatment, laboratory tests, and other study procedures.

8.2 Exclusion Criteria

Patients meeting any one of the followings are not eligible to participate in this study:

1. Those who have received the following treatments within 4 weeks prior to C1D1:
 - Previously received radiotherapy, surgery, chemotherapy, immune or molecular targeted therapy for tumors;
 - Received other investigational drug of clinical studies;
 - Inoculated with a live attenuated vaccine.
2. Subjects who previously received anti-PD-1/PD-L1/CTLA4 antibodies, or VEGFR single target/multiple target inhibitors.
3. Those who plan to receive surgical treatment and/or radiation therapy for soft tissue sarcoma during the study period.
4. Presence of tumor lesions in the central nervous system confirmed by imaging diagnosis.
5. Having been treated by immunosuppressive drugs within 14 days prior to C1D1, excluding intranasal and inhaled corticosteroids or systemic steroids of physiological doses (i.e., no more than 10 mg/d of prednisolone or equivalent physiological doses of other corticosteroids).
6. Presence of any active autoimmune diseases or a history of autoimmune diseases (including but not limited to: autoimmune hepatitis, interstitial pneumonia, uveitis, enteritis, hepatitis, hypophysitis, vasculitis, nephritis, hyperthyroidism, hypothyroidism; adult patient with vitiligo or completely relieved childhood asthma may be enrolled if they do not require any intervention), or known history of allogeneic organ transplantation or allogeneic hematopoietic stem cell transplantation.

7. Complicated with severe infection (such as one requiring intravenous drip infusion of antibiotics, antifungals, or antivirals) within 4 weeks prior to C1D1, or any unexplained fever of > 38.5 °C during screening/prior to the first dose.
8. Hypertension uncontrolled by antihypertensives (systolic pressure > 140 mmHg or diastolic pressure > 90 mmHg).
9. Patients with clinically significant bleeding symptoms or a clear bleeding tendency within 3 months prior to C1D1, such as hemorrhage of digestive tract, stomach ulcer with hemorrhage, fecal occult blood ++ and above at baseline, or vasculitis; or arterial/venous thrombus events, such as cerebrovascular accidents (including transient ischemic attack, cerebral hemorrhage, and cerebral infarction), deep vein thrombus, pulmonary embolism, etc. within 6 months before C1D1; or requiring long-term anticoagulation therapy with warfarin or heparin, or requiring long-term antiplatelet therapy (aspirin ≥ 300 mg/d or clopidogrel ≥ 75 mg/d).
10. Active heart diseases within 6 months before C1D1, including myocardial infarction, severe/unstable angina, etc. Left ventricular ejection fraction $< 50\%$ as revealed by echocardiography and poorly controlled arrhythmia (including QTcF interval > 450 ms in males and > 470 ms in females).
11. Having been diagnosed with any other malignancies within 3 years before C1D1, excluding adequately treated basal cell carcinoma and squamous cell skin cancer, and cervical carcinoma in situ.
12. Known allergies to the study drug or their excipients; severe allergic reactions to other monoclonal antibodies.
13. With human immunodeficiency virus (HIV) infection, or active hepatitis B (positive hepatitis B surface antigen and HBV DNA ≥ 500 IU/mL) or hepatitis C (positive for hepatitis C antibody, and HCV-RNA higher than the lower limit of detection of the analytical method).
14. Presence of accompanying diseases (such as poorly controlled hypertension, severe diabetes, neurological or mental illness, etc.) or any other situation that may pose serious risks to the safety of the subjects, confuse the research results, or affect the ability of the subjects to complete the study as judged by the investigator.

8.3 Withdrawal from Study or Treatment Discontinuation

8.3.1 Study withdrawal criteria

Reasons for withdrawal may include:

- Withdrawal of informed consent and refusal of further follow-ups by subjects;
- Other investigator-assessed reasons requiring withdrawal, such as the inability to provide voluntary consent due to imprisonment or quarantine;
- Lost to follow-up;
- Death;
- Study termination by the sponsor.

8.3.2 Criteria for treatment discontinuation

The study treatment must be discontinued when any of the following occurs:

1. Treatment discontinuation requested by subjects;
2. Radiographic (assessed by the investigator as per RECIST v1.1) or clinical progression, except for the following two situations: 1) The subjects in the investigational treatment group meet the criteria for continuing treatment beyond progression (see 8.3.3 for details); 2) The subject in the control group who had radiographic progression and meet the inclusion/exclusion criteria may be crossed over to receive the SHR-1210 + apatinib treatment (see 8.3.4 for details);
3. Occurrence of subject pregnancy during the study;
4. Any clinical AEs, laboratory abnormalities, or other medical conditions indicating that the subject can no longer benefit from the treatment;
5. General deterioration of health status and inability to continue study participation;
6. Major protocol deviations such as ineligibility found after enrollment;
7. Lost to follow-up;
8. Study termination by the sponsor.
9. Death;
10. Other reasons as determined by the investigator.

8.3.3 Criteria for continuing treatment beyond progression (investigational treatment group)

Some subjects receiving immunotherapy or anti-angiogenesis therapy can still benefit from continuing treatment after radiographic progression. The tumor of some subjects may be enlarged, but remarkable necrosis, denaturation, or infiltration of immune cells may occur inside the tumor, with CT showing decreased internal density of the tumor lesion. It is generally considered to be beneficial to subjects under this circumstance. A subject meeting the following criteria may continue the treatment after progressive disease (PD, as per the investigator's judgment) based on RECIST v1.1:

- The investigator deems that it is in the best interest of the subject to continue treatment, and subject is not required to start other anti-tumor treatment immediately;
- The subject is able to tolerate continued study treatment;
- No obvious deterioration in subject's performance status, and no marked worsening of cancer-related symptoms;
- Subjects must sign the informed consent form prior to continuing study treatment, in which potential risks, discomforts, and other treatment options shall be included;
- Continued study treatment must be reviewed and approved by the principal investigator of the study center.

The assessment of clinical benefit must consider whether the subject has clinical exacerbations and whether the subject can benefit from continuing treatment. It is recommended that the investigator should discuss with the sponsor whether the subject should continue treatment beyond progression.

If it is decided that the subject will continue the study treatment after progression, the subject should continue to be treated and followed up according to the protocol requirements.

Investigators at the study center will perform subsequent imaging evaluations as per iRECIST (see Appendix 11) (independent imaging evaluations will still be performed as per RECIST v1.1).

Subjects should withdraw from the study if the subject has iRECIST-confirmed PD (iCPD) in the subsequent tumor evaluation. The initial date of investigator-assessed progression should be used for the statistical analysis of PFS in secondary endpoints, regardless of whether the subject continues the study treatment beyond progression.

If the subject discontinues treatment due to deterioration of the general condition without objective evidence for progressive disease, the progression will be reported as "general deterioration". More objective evidences (e.g., imaging confirmation) of progressive disease of these subjects should be obtained whenever possible after treatment discontinuation.

8.3.4 Criteria for crossover treatment of subjects in control group after radiographic progression

In a subject in the control group is found to have PD during or after chemotherapy, the safety visit will be conducted. After completing relevant examinations, subjects who are willing to and eligible for crossover treatment may be crossed over to receive the treatment of SHR-1210 combined with apatinib.

If the inclusion and exclusion criteria are not met, the subject may receive supportive treatment for adjustment. But during this period, anti-tumor treatment must not be performed. If, at the reexamination 2 months after progressive disease, the inclusion and exclusion criteria are still not met, crossover to receive SHR-1210 combined with apatinib will not be permitted.

For the schedule of activities for the crossover treatment period and subsequent follow-ups of the control group, please refer to "3. Schedule of activities - crossover treatment" for details.

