11.3.3 Survival follow-up

The survival follow-up period starts after the end of the safety follow-up period. The survival follow-up period ends upon the subject's death, lost to follow-up, withdrawal of informed consent, or study termination by sponsor. During this period, an effective follow-up such as telephone follow-up will be conducted once every 2 months to collect information on subject survival and subsequent treatments (if the subject has started a new anti-tumor treatment, the therapeutic regimen and the start and end time should be recorded).

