12 EVALUATIONS

12.1 Efficacy Evaluation

In addition to the investigator's assessments of the tumor imaging results in this study, the sponsor will also collect all imaging results (except for the imaging results of the control group after crossover treatment), and use them for blinded independent review (all per RECIST v1.1). The specific procedures for independent review are described in the "Third-Party Independent Review Charter" for this study, written by the central imaging.

PFS: the time between the date of enrollment and the date of the first documented tumor progression (as per RECIST v1.1, regardless of whether treatment is continued), or death from any cause, whichever occurs first.

In addition, subjects in the investigational treatment group will continue the study treatment after progressive disease. The investigator will perform subsequent imaging assessments as per iRECIST (see Appendix 11; independent imaging evaluation is still carried out as per RECIST v1.1) for exploratory evaluation of PFS in the investigational treatment group as per iRECIST. PFS is defined as the period of time from the date of the subject's enrollment to the first iUPD that can be subsequently confirmed or the date of death due to any cause, whichever occurs first. The imaging evaluation criteria of the control group after crossover treatment are the same as those of the investigational treatment group, but no independent review of central imaging will be performed. The subjects after crossover will be analyzed based on the PFS data as per RECIST v1.1 and iRECIST.

OS: the time from the date of enrollment to the date of death from any cause. Subjects whose final status is "survived" are censored, and the date of censoring is the date of the last follow-up.

ORR: the proportion of treated subjects whose best overall response (BoR) is complete response (CR) or partial response (PR) as per RECIST1.1.

DCR: the proportion of treated subjects whose best overall response is complete response (CR), partial response (PR), or stable disease (SD) as per RECIST v1.1.

DoR: the period of time from the first documented tumor response (as per RECIST v1.1) to the first documented objective progression (as per RECIST v1.1) or death of any cause.

iORR: the proportion of treated subjects whose best overall response (BoR) is complete response (CR) or partial response (BOR) as per iRECIST v1.1.

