14.4.3 Secondary efficacy endpoint analysis

The analysis of secondary efficacy endpoints will be based on the FAS.

For the secondary endpoint PFS assessed by the investigator (as per RECIST v1.1), the analytical method will be the same as that of the primary endpoint mentioned above.

The secondary endpoint OS will be statistically described using the similar method for the primary endpoint. For DoR, the Kaplan-Meier method will be used to plot the survival curve and estimate the median DoR and its 95% confidence interval will be calculated (Brookmeyer-Crowley method).

For the objective response rate (ORR) and disease control rate (DCR), the rates in the two groups and their two-sided 95% CI (Clopper-Pearson method) will be estimated, and the inter-group difference of rates and its two-sided 95% CI will be calculated (CMH method).

Other endpoints will be statistically summarized in accordance with general principles.

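### Protocol 8.3.3 tells subjects who reach confirmed iRECIST progression to leave the study, which conflicts with the treatment-discontinuation and survival follow-up rules and creates a risk of informative OS censoring

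*Protocol*

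**What the plan says.** Protocol 8.3 separates two things. Section 8.3.1 lists reasons for withdrawal from the study, the first being "Withdrawal of informed consent and refusal of further follow-ups by subjects". Section 8.3.2 lists reasons for stopping treatment, and progression appears there: "Radiographic (assessed by the investigator as per RECIST v1.1) or clinical progression, except for the following two situations". The first of those two situations is treatment beyond progression in the investigational group under 8.3.3. To enter that path a subject must, among other conditions, show "No obvious deterioration in subject's performance status, and no marked worsening of cancer-related symptoms". Section 8.3.3 then closes the path: "Subjects should withdraw from the study if the subject has iRECIST-confirmed PD (iCPD) in the subsequent tumor evaluation".

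On follow-up, Protocol 11.3.3 says: "The survival follow-up period ends upon the subject's death, lost to follow-up, withdrawal of informed consent, or study termination by sponsor". The synopsis, section 7.1, note [25] to the investigational-group schedule and SAP 2.1 give the same rule, with contacts every two months. Section 11.3.1 runs safety follow-up to 90 days after the last dose.

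OS is a secondary endpoint in Protocol 6.2.2. Section 12.1 defines its censoring: "Subjects whose final status is 'survived' are censored, and the date of censoring is the date of the last follow-up". Section 14.4.3 gives its analysis: "The secondary endpoint OS will be statistically described using the similar method for the primary endpoint". The SAP's secondary objectives (2.2.2), secondary endpoints (4.1.2) and secondary analyses (5.4.2) do not include OS.

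**The concern.** The 8.3.3 sentence applies the study-withdrawal term to a progression event, which the rest of section 8.3 handles as a treatment matter. A site that takes it at face value closes the subject's participation at iCPD. Under 12.1 that subject's OS is then censored at about that date, just after tumour growth has been confirmed a second time. Censoring at that moment is plausibly related to the risk of death, so it cannot be assumed non-informative.

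The heading of 8.3.3 confines the rule to the investigational group, and 8.3.4 has no matching sentence for control subjects at progression. Any loss of deaths would therefore fall mainly in one arm of an open-label comparison. The remaining safety contacts at 30, 60 and 90 days, and the record of subsequent anti-tumour treatment, could be lost as well. Survival status that was not collected at the time may be hard to recover later.

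**Working it through.** **1. The passages side by side, for an investigational subject with iCPD.**

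| Place | What it implies |
|---|---|
| 8.3.3 | Leave the study |
| 8.3.2, item 2 | Progression is a treatment-discontinuation criterion, and 8.3.3 is an exception to it |
| 8.3.1 | iCPD is not listed, but the list is open and has a catch-all for investigator-assessed reasons |
| 11.3.1 | Safety follow-up to 90 days after the last dose |
| 11.3.3, 7.1, synopsis, schedule note [25] | Survival follow-up continues, and iCPD is not among its end points |

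The conflict is between 8.3.3 on one side and 8.3.2, 11.3.1 and 11.3.3 on the other. Section 8.3.1 does not settle it. Its open wording neither names iCPD nor stops a site from recording it as a withdrawal.

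**2. The plan's own figures.** The only sizing is for IRC-assessed PFS. With HR 0.64, one-sided alpha 0.025 and 90% power, the fixed-design count is 4 × (1.960 + 1.282)² / (ln 0.64)² = 211.0, or 212 events. With the O'Brien-Fleming-type look at 143 of 214 events (boundaries 2.506 and 1.993), 90% power needs 213.5, so 214 reproduces. Then 262 / 0.9 = 291.1, so 292 reproduces. None of this depends on follow-up after progression. The documents state no OS event target or OS power to recompute.

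**3. Illustration of the OS effect.** Inputs from the documents:
- control median PFS 4.5 months, and 20 months of accrual (14.1);
- data cut at 26 + 12 = 38 months (14.1 and 8.4);
- confirmation 4 to 8 weeks after iUPD (Appendix 11), taken as 6 weeks, about 1.4 months.

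Assumptions:
- exponential times, with progression before every death;
- median PFS of 4.5 months in both arms, so no true PFS effect;
- post-progression median of 6 months, giving a median OS of about 12.6 months, close to the roughly one year mentioned in 5.3;
- a share f of the investigational arm marked to leave 1.4 months after progression if still alive;
- marked subjects have either average prognosis or a post-progression median 1.5 times longer (9 months).

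The Cox hazard ratio (investigational/control) was computed on 40,000 simulated subjects per arm. Simulation noise is about 0.01.

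| f | Average prognosis: full follow-up → literal 8.3.3 | Ratio | Better prognosis: full follow-up → literal 8.3.3 | Ratio |
|---|---|---|---|---|
| 5% | 1.007 → 0.994 | 0.99 | 0.982 → 0.985 | 1.00 |
| 10% | 0.992 → 0.962 | 0.97 | 0.966 → 0.965 | 1.00 |
| 20% | 0.998 → 0.937 | 0.94 | 0.925 → 0.922 | 1.00 |
| 30% | 0.994 → 0.899 | 0.90 | 0.915 → 0.895 | 0.98 |
| 50% | 1.013 → 0.826 | 0.82 | 0.851 → 0.786 | 0.92 |

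The ratio is the literal-reading HR divided by the full-follow-up HR. In the better-prognosis columns the longer survival is added to the investigational arm, so the full-follow-up HR falls below 1. The bias is the change within a row, not the distance from 1.

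**The case against.** The best defence is that the word is used loosely. Section 8.3.3 concerns continuing treatment, and it is cited in 8.3.2 as an exception to stopping treatment, so its last step reads naturally as the end of that exception. The Protocol is loose with the same word elsewhere. Section 13.3 has a pregnant subject withdraw, while 8.3.2 lists pregnancy as a treatment-discontinuation reason and 12.2.1 keeps her under observation after dosing stops. Several consistent statements keep survival follow-up running, against one sentence. This is probably what was meant, but it does not remove the instruction a site will read.

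A reader might infer that the Protocol ends survival follow-up for the sickest investigational subjects. The documents do not support either part. Section 11.3.3 and its parallels keep follow-up open, so the accurate finding is a contradiction. The sentence reaches only subjects treated beyond progression, who were selected at first progression for no obvious deterioration. Subjects who stop at first progression are outside it. That screen applies at first progression rather than at iCPD, so it does not show that they still have a good prognosis by then.

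The one-arm framing is also uncertain. Crossover subjects have the same imaging criteria (12.1) and the same treatment and follow-up visits (11.4.2, 11.4.3) as the investigational group. A site might apply the sentence to them too, which could reduce the asymmetry but would lose more survival data.

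Finally, OS carries no alpha and is absent from the SAP's endpoints. That limits the consequence. It stays a comparative secondary objective in Protocol 6.1.2, and 8.4 ties study completion partly to OS data.

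**Conclusion.** The contradiction is real, and its severity is low to moderate. If sites follow 8.3.3 literally, OS would be censored at confirmed progression, mainly in the investigational arm, and the bias would tend to favour that arm. Under the stated assumptions it runs from negligible (up to about 20% of the arm, if those subjects have better prognosis) to material (HR about 0.90 instead of 1.00 at 30%, with average prognosis). The direction is a tendency: strong enough selection for good prognosis can cancel the shift.

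No single bias figure should be quoted. The share reaching iCPD and their prognosis are not in the documents, and large shares withdrawn at random would overstate what can be known. Nothing shows that the sponsor chose to stop survival follow-up.

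The primary analysis is untouched. It uses IRC review under RECIST v1.1, and the 214 events, 262 and 292 subjects stand. Investigator-assessed PFS is also protected, because 8.3.3 itself fixes the initial progression date for that endpoint.

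**What to change.** Reconcile 8.3.3 with 8.3.1, 8.3.2 and 11.3.3. State that iCPD is not in itself a withdrawal from the study, and that safety follow-up (11.3.1) and survival follow-up (11.3.3) continue until one of their own end points is met. Say explicitly whether the sentence also applies to control subjects after crossover. If any subject has already been recorded as withdrawn at iCPD, list them by arm and seek survival status where consent allows.

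The cost is one or two sentences and a note to sites. The two-monthly contacts are already planned, and no sample size or analysis changes. This concerns follow-up data only. The rule on treatment at iCPD is not judged here.
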